the effects of submaximal EMS exercises. The study was approved by the Ondokuz Mayıs University Clinical Research Ethics Committee (approval number: 021/482) and was conducted as per the ethical principles stated in the Declaration of Helsinki. The inclusion criteria of the participants were determined as being between the ages of 19-24, being female, and volunteering. Exclusion criteria were those who had cardiovascular, neurological, or orthopedic disorders, were pregnant or were planning to become pregnant. Subjects made a total of 10 visits, including the familiarization session for the study. During the first visit, participants were informed about test protocols. Anthropometric measurements were then taken and trial measurements were made. In the pre-, mid (week 4), and post (week 8) test periods, all participants performed 3 visits at 24-hour intervals for a total of 9 visits according to the test protocols they selected from the practice cards specified for each period, and mid and post-tests were arranged so that they did not coincide with training days. Practice cards were as follows: 1- modified push-up (MPU), Handgrip strength (HS), single hop for distance (SH), Biering Sorensen (Bie-sor), 2- Bent arm hanging (BAH), triple hop for distance (TH), crossover triple hop for distance (CH), v-sit flexor (V-sit) and 3- deep squat (DS), medial side triple hop for distance (MSTH), sit-up. After completion of the pre-tests, participants were randomized into one of two exercise groups using computer-validated software (www.random.org) and divided into EMS (n=15) and Control (CON) (n=16) groups. Participants who did not participate in regular exercises and tests in both groups were excluded from the study and the study was completed with 12 participants for the EMS group and 15 participants for the CON group. All measurements and exercises were done at the same time of the day (12:00-16:00). The participants performed warm-up exercises before the tests. Both groups were asked not to make any changes in their usual physical activity behavior. Also, all participants were instructed to maintain their normal dietary intake before and during the study. The endpoint of the study was determined as the participant withdrawing consent to participate in the study, the experts deciding that it was not appropriate for the participant to continue in the study, and non-compliance with the study protocol.

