The measurements were made using a hand dynamometer that can measure force between 0-100 kilograms, and the dynamometer was adjusted according to the hand of the athlete to be measured before the measurement. The person to be measured was asked to squeeze with maximum force while standing, with arms hanging down so that the dynamometer did not touch the body. 3 measurements were made, with 1 minute of rest between measurements, and their averages were recorded (Melo et al., 2025).

Bent Arm Hanging Test (BAH)

This test was based on the measurement of the hanging time of the athletes with their arms in full flexion (elbow joint angle less than 75°). During the test, the athlete was verbally warned to remain in the position in question. The test was terminated when the participant's chin dropped below the bar level. The test result was recorded with a CASIO timer as the time the participant could hang under defined conditions (Clemons, 2014).

Single Leg Hop Tests (SLHT)

SLHTs were implemented on a single line by the parameters SH, TH, CH, and MSTH (Reid et al., 2007; Kivlan et al., 2013). For the line to be used in the test, a 0.3 m strip was determined as the starting point, and a 6 m long and 5 cm wide strip extending from the middle was placed vertically. Before starting the test, the test protocol was shown to the subjects verbally and practically. Each participant performed 1 trial forward from the baseline for each test and each limb. They then performed 3 trials for the actual test and the result was recorded in cm. A 30-second rest was given between trials. The best-recorded score was measured between the baseline and the subject's heel. No restrictions were made on arm swings. After the jump, care was taken to ensure that the subject was on the line in the limb that was tested in a controlled manner. The test was repeated if the subject lost balance landed on a limb different from the test limb, or made an additional jump after landing (Kehribar et al., 2022).

Deep Squat Test (DS)

In the deep squat test, individuals place their feet shoulder-width apart with their toes pointing straight ahead. On command, participants stand in the lowest squat position they can reach without lifting their heels off the floor. Although each individual has three attempts, if they complete the test on the first attempt, they do not need to repeat the test (Stanton et al., 2021).

V-Sit Flexor Test

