For the V-sit flexor endurance test, testing the endurance of the flexor muscles began with the person being placed in a sitting position and leaning on a jig with the back at an angle of 55

degrees from the floor. Knees and hips were flexed 90 degrees, arms folded across the chest, and feet secured under the strap. To start, the jig was pulled back 10 cm (4 inches) and the person tried to hold it as long as possible without disturbing the posture of the body. Failure in the test was determined to occur when the subject's back was touched or when the subject was asked to stop (Chai et al., 2024).

Sit- Up Test

In the sit-up test, the participant lay on their back on a gymnastics mat and locked their hands behind their neck. The sole was fixed to the mat with the knees at a fixed angle (90°). An aid was used to stabilize the sole. The number of sit-ups the subject would perform for 30 seconds was recorded (Kukic et al.,2022).

Biering Sorensen Test (Bie-sor)

For the Biering-Sorensen-back extensor test, the upper body was extended over the end of a stretcher and then the pelvis, knees, and hips were fixed. The test began after the hands were fixed crosswise on the chest. Failure in the test occurred when the upper trunk broke its horizontal position when it failed to maintain its position after a verbal warning, and when the participant requested to stop (Nuzzo & Mayer, 2013).

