## **The Effect of Electrical Muscle Stimulation Exercise on Lower, Upper Extremity, and Core Strength in Sedentary Women**

### **Statistical Analysis**

SPSS 21.0 package program was used for data analysis. The normality assumption of the data was examined with the Kolmogorov-Smirnov test and it was determined that the variables were normally distributed ( $p>0.05$ ). One-way analysis of variance in repeated measures and Mixed Design Analysis of Variance in Repeated Measures were applied to the data. Sphericity was examined with Mauchly's Sphericity test. The Sphericity Assumed test was used for those with equal variances ( $p>0.05$ ). In cases where variances were not equal ( $p<0.05$ ), the epsilon value ( $\epsilon$ ) was examined and Greenhouse and Geisser tests were used when  $\epsilon<0.75$  and Huynh-Feldt tests were used when  $\epsilon>0.75$ . Bonferroni test was used to determine the intergroup differences. Data were presented as mean and standard deviation and evaluated at a significance level of  $p<0.05$ .

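### Does the unstated deep squat score make its ANOVA unsafe?

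*Protocol*

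**What the plan says.** The Protocol (Study Design) puts the deep squat on the third practice card, "3- deep squat (DS), medial side triple hop for distance (MSTH), sit-up", and all tests are done before training, at week 4 and at week 8. Under Procedures, Deep Squat Test (DS), the instruction is that "participants stand in the lowest squat position they can reach without lifting their heels off the floor". The attempt rule follows: "Although each individual has three attempts, if they complete the test on the first attempt, they do not need to repeat the test". A source is cited for the test. No depth, angle, time, grade or pass/fail result is named.

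Other tests are more explicit. For handgrip, "3 measurements were made, with 1 minute of rest between measurements, and their averages were recorded". For the hops, "They then performed 3 trials for the actual test and the result was recorded in cm", with the best score kept. For the sit-up, "The number of sit-ups the subject would perform for 30 seconds was recorded".

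The SAP (Statistical Analysis) makes no exception for any test: "The normality assumption of the data was examined with the Kolmogorov-Smirnov test and it was determined that the variables were normally distributed". Repeated-measures and mixed-design ANOVA are applied, and "Data were presented as mean and standard deviation".

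**The concern.** A mean and SD need a scale, and the deep squat has none on paper. Its two key sentences can be read as pulling apart. The lowest position a person can reach sounds like a depth, which everyone attains to some degree. Completing the test on the first attempt sounds like a pass or a grade. The number of attempts, one to three, varies with performance, and no sentence says which attempt is entered.

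If the score were a coarse grade, a blanket normality statement would be doubtful for it, a mean and SD would describe it poorly, and an ordinal or categorical comparison might be preferable. If it were a depth, choosing the first, best or last attempt might alter the size of the group difference. At stake is whether a reader can interpret the deep squat result at all.

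**Working it through.** No figure in the plan depends on the deep squat score, so there is none to reproduce. The check is a comparison of texts plus four calculations. All score shapes, reliabilities and pass marks below are assumptions, because the documents give no outcome data.

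**1. How wide is the gap?** The practice cards list 4 + 4 + 3 = 11 tests.

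| Tests | Recorded quantity |
|---|---|
| Push-up, sit-up | Count in 30 s, stated |
| Handgrip | Average of three, stated |
| Bent arm hang | Time, stated |
| Four hop tests | Best distance in cm, stated |
| V-sit, Biering-Sorensen | Not stated; both are holds ended by failure, so a time is implied |
| Deep squat | Neither stated nor implied |

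That is 8 stated, 2 implied and 1 open.

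**2. Do the two deep squat sentences conflict?** Not necessarily. The instruction carries its own condition: the heels stay on the floor. On a natural reading, an attempt with heels down is complete, and one with a heel lift is tried again, up to three times. The extra attempts are then validity repeats, like the hops that are redone after a loss of balance. The attempt that counts is the completed one. Two things stay open: the unit, and what is entered if all three attempts fail.

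**3. If the score is a depth, does the attempt rule matter?** Model: attempt = true value + error, total SD 1; reliability 0.70, 0.80, 0.90 or 0.95; pass mark at -1, -0.5, 0, 0.5 or 1 SD from the control mean; stop at the first pass, with at most three attempts. This gives 4 × 5 = 20 settings, with 200,000 simulated participants per arm and a true difference of 0.80 SD.

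| Attempt recorded | Difference in single-attempt SDs | Difference ÷ SD of the recorded score |
|---|---|---|
| First | 0.80 | 0.80 |
| Best | about 0.65 to 0.78 | 0.78 to 0.83 |
| Last | 0.72 to 0.86 | 0.78 to 0.82 |

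The middle column seems to show a loss when the best attempt is taken. That is mostly a matter of units: repeating until a pass also narrows the spread of the recorded scores. The F test compares a difference with the recorded score's own SD, which is the last column, and there the rule hardly matters.

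**4. If the score is coarse, does the planned test mislead?** Groups of 12 and 15, three time points, latent correlation 0.7, 20,000 null trials per shape, and the SAP's rule of Mauchly's test followed by Greenhouse-Geisser or Huynh-Feldt. Rejection of the group-by-time effect at the nominal 5% was 4.9% for a continuous score, 4.7% to 5.0% for three or four levels, and 4.2% to 4.9% for pass/fail with 30% to 80% passing. There is no inflation under any shape tried.

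**5. Is the normality statement informative?** The SAP does not say which form of the Kolmogorov-Smirnov test was used. Share of simulated samples rejected at 0.05 (2,000 runs per setting):

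| Assumed score | n = 12 | n = 15 | n = 27 |
|---|---|---|---|
| 3 levels, Lilliefors-corrected | 83–97% | 86–99% | 100% |
| 3 levels, uncorrected | 5–18% | 8–43% | 55–95% |
| Pass/fail (50% or 80% passing), corrected | 100% | 100% | 100% |

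For pass/fail the uncorrected test also rejects in every sample at n = 15 and n = 27. Taken at face value, then, the SAP's statement that the variables passed speaks against a pass/fail score. It also speaks against a three-level score if the corrected test was used. It does not prove a continuous scale.

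**6. Does a mean and SD hide the data?** On a score of 0 to 3 graded by attempt, different count patterns can share a mean and SD. With 12 participants, 0/9/0/3 has mean (9×1 + 3×3)/12 = 1.50, and 3/0/9/0 has mean (9×2)/12 = 1.50. Each has a sum of squares of 9, so SD = √(9/11) = 0.90. The arithmetic is right, but no sentence in the documents suggests such a scale, so it does not measure a defect in this plan.

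**The case for a change.** The strongest case for a change is that the authors set their own standard. They say what is recorded for eight tests, and they give a rule for combining trials for grip and for the hops. Only for the deep squat can a reader neither find nor infer the quantity, and the cited source, which may define it, does not show which score this study entered. Robust error rates do not help someone who wants to know what a mean difference measures. The remedy would be a sentence or two from existing records.

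Much of this stands: the quantity, its unit and the entry after three failed attempts are not written down. What does not stand is the step from there to the analysis. The normality statement cannot be verified for any of the 11 tests, because the SAP reports no result by variable and the documents hold no outcome data; the deep squat is not special in that respect. A switch to counts and an ordinal test would depend on a scale that nothing in the text establishes. The Protocol describes the study as completed, so such a test would also be post hoc.

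**Conclusion.** No change to the plan follows. This is a missing measurement detail in 1 of 11 tests, of the kind that is settled from the test records and stated when results are reported with their units. No analysis error is shown. The planned test's simulated false-positive rate stays at 4.2% to 5.0% under every score shape tried. If the score is a depth, the choice of attempt moves a 0.80 SD difference only to between 0.78 and 0.83 on the scale the F test uses. No main conclusion is shown to depend on the missing detail.

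This rests on the assumed reliabilities, pass marks and score shapes, and on reading the heels-down condition as what makes an attempt complete. That reading is natural but not the only one. If the records showed a categorical score, the way it is summarised would deserve a fresh look; the documents give no ground to presume so.

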## **The Effect of Electrical Muscle Stimulation Exercise on Lower, Upper Extremity, and Core Strength in Sedentary Women**

### **Statistical Analysis**

SPSS 21.0 package program was used for data analysis. The normality assumption of the data was examined with the Kolmogorov-Smirnov test and it was determined that the variables were normally distributed ( $p>0.05$ ). One-way analysis of variance in repeated measures and Mixed Design Analysis of Variance in Repeated Measures were applied to the data. Sphericity was examined with Mauchly's Sphericity test. The Sphericity Assumed test was used for those with equal variances ( $p>0.05$ ). In cases where variances were not equal ( $p<0.05$ ), the epsilon value ( $\epsilon$ ) was examined and Greenhouse and Geisser tests were used when  $\epsilon<0.75$  and Huynh-Feldt tests were used when  $\epsilon>0.75$ . Bonferroni test was used to determine the intergroup differences. Data were presented as mean and standard deviation and evaluated at a significance level of  $p<0.05$ .

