Official Title: The Effects of Electrical Muscle Stimulation Exercise on Upper, Lower Extremity and Core Strength in Sedentary Women

NCT Number: Pending

Date: October 7, 2025

Prepared by: [name] [name]

[name]

Institution: 19 Mayıs University

The Effect of Electrical Muscle Stimulation Exercise on Lower, Upper Extremity, and Core Strength in Sedentary Women

Participants

Our study was conducted with 27 sedentary women between the ages of 19-24. The optimal number of subjects to participate in the study was determined using the GPower 3.1.3 program. The results indicated that a total of 16 subjects would be an appropriate sample size for the study (effect size r : 0.87, lower and upper critical p : 0.53, true power: 0.92). Before the study, the subjects were informed in detail and included in the study by obtaining an "Informed Consent Form".

[figure not shown]

Figure 1. Flowchart

Study Design

This study was designed as a 2-arm parallel-group randomized controlled trial comparing

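### The main between-group result should be the week-8 EMS-minus-CON difference adjusted for the pre-test, not an ANOVA that treats the pre-randomisation test as an outcome level

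*SAP*

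**What the plan says.** The Protocol (Study Design) states: "This study was designed as a 2-arm parallel-group randomized controlled trial comparing" submaximal EMS exercise. On timing it says "In the pre-, mid (week 4), and post (week 8) test periods, all participants performed 3 visits", and on allocation "After completion of the pre-tests, participants were randomized into one of two exercise groups". The pre-test therefore precedes assignment and cannot be affected by it. Participants were "divided into EMS (n=15) and Control (CON) (n=16) groups", and "the study was completed with 12 participants for the EMS group and 15 participants for the CON group".

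The SAP (Statistical Analysis) then says "One-way analysis of variance in repeated measures and Mixed Design Analysis of Variance in Repeated Measures were applied to the data". It gives rules for sphericity and adds "Bonferroni test was used to determine the intergroup differences", with a 0.05 significance level. The visible text does not say which model or term answers the EMS-versus-CON question, at which visit, or whether the one-way ANOVA is run within each arm. Part of the SAP was removed before review, so this absence holds for the visible text only.

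**The concern.** Randomisation supports one kind of statement: how the arms differ after assignment. Neither model, as described, delivers that as an estimate.

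- **One-way repeated-measures ANOVA.** With no group factor it describes change over time and cannot compare EMS with CON. Running it within each arm is a plausible reading, but the SAP does not say so.
- **Mixed ANOVA, group main effect.** This averages three test periods, one of which can carry no treatment effect. Read as the EMS effect, it is too small by construction.
- **Mixed ANOVA, group-by-time interaction.** This is a legitimate comparison of arms, but a significant result says only that the profiles differ somewhere. It gives no size in test units.
- **Bonferroni.** Two arms form one pair, so the correction factor for comparing arms is 1 unless comparisons are taken over visits. No visit is given.

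At stake are the size and precision of the reported effect in a trial with 27 analysed participants. The pre-test values that would sharpen the estimate are already in hand.

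**Working it through.** **Inputs from the documents:** 12 EMS and 15 CON analysed; three test periods; alpha 0.05; the SAP's sphericity rule (cut-off 0.75).

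**Assumptions, because the documents give no SDs, correlations or target difference on these tests:** normal data, equal variances (SD = 1), two-sided tests, and an EMS effect of 0.8 SD at week 8. The effect either builds linearly (0, 0.5, 1 of its full size at the three tests) or is full by week 4 (0, 1, 1). There are eight correlation cells: compound symmetry (CS) and AR(1), each at 0.5, 0.7, 0.8 and 0.85. Simulated figures use 20,000 trials per cell (Monte Carlo error at most 0.4 points). The plan has no figure of its own on this point to reproduce.

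**1. What the group main effect estimates**
- Linear: 0.8 × (0 + 0.5 + 1)/3 = 0.40 SD, one-half of the week-8 effect.
- Full by week 4: 0.8 × (0 + 1 + 1)/3 = 0.53 SD, two-thirds.

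**2. Its power** (noncentral t, 25 df). SE = √[ΣV/9 × (1/12 + 1/15)] = √[ΣV/9 × 0.15], where ΣV is the sum of all entries of the 3 × 3 correlation matrix.
- Smallest ΣV, AR(1) 0.5: 5.5, SE 0.303, power 24.6% (linear) and 39.5% (full by week 4).
- Largest ΣV, CS 0.85: 8.1, SE 0.367, power 18.2% and 28.7%.
- The other six cells lie between these.

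**3. Error rate with no EMS effect**
- The interaction alone rejects in 4.7-5.6% of trials.
- If either the interaction or the group main effect could count as success, 9.4-10.3% per outcome (check: 1 − 0.95² = 9.75%).

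**4. Precision of the week-8 contrast: change score against pre-test-adjusted.** With r the correlation between pre-test and week 8, the approximate 95% half-widths are 2.06 × √[2(1 − r) × 0.15] and 2.06 × √[(1 − r²) × 0.15]. At r = 0.5 these give 0.80 and 0.69 SD. The simulated means, which allow for the estimated SD and chance pre-test imbalance, are 0.79 and 0.70.

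| Cell | Change score | Adjusted |
|---|---|---|
| CS 0.5 | 0.79 | 0.70 |
| CS 0.7 | 0.61 | 0.58 |
| CS 0.85 | 0.43 | 0.42 |
| AR(1) 0.5 | 0.97 | 0.78 |
| AR(1) 0.7 | 0.80 | 0.70 |
| AR(1) 0.8 | 0.67 | 0.62 |
| AR(1) 0.85 | 0.59 | 0.56 |

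**5. Power of the adjusted week-8 contrast minus power of the interaction (percentage points)**

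| Cell | Linear | Full by week 4 |
|---|---|---|
| CS 0.5 | +19.6 | +7.9 |
| CS 0.7 | +14.3 | +0.5 |
| CS 0.8 | +7.8 | −1.9 |
| CS 0.85 | +4.4 | −1.5 |
| AR(1) 0.5 | +16.6 | +6.2 |
| AR(1) 0.7 | +10.8 | −2.1 |
| AR(1) 0.8 | +7.4 | −7.7 |
| AR(1) 0.85 | +4.5 | −8.9 |

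For scale, linear power of the interaction and of the adjusted contrast is 42% and 61% at CS 0.5, and 76% and 80% at AR(1) 0.85.

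**The case against.** The strongest reply is that the plan already contains a sound test. The mixed ANOVA's interaction compares the arms and holds its error rate. The sphericity rules that fill most of the SAP apply to within-subject terms, which include the interaction but not the group main effect, so the main effect is the less natural reading. This stands: if the only defect were that the interaction is not named, one clarifying sentence would do.

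It is also fair that the adjusted contrast is not uniformly more powerful. When the effect is full by week 4, it loses to the interaction in five of the eight cells. The case for it rests on giving one interpretable estimate with a CI, and on its gain when the effect builds up.

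A reader might infer three stronger things that the documents do not support:

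- **That the plan doubles its false-positive rate.** The 9-10% figure needs a rule that either group term counts as success. No such rule is stated.
- **That the EMS claim rests on within-arm change alone.** The SAP does not say this. How misleading within-arm change would be depends on what CON did, and that is ambiguous. The Protocol speaks of two exercise groups, yet describes no CON programme and says "Both groups were asked not to make any changes in their usual physical activity behavior".
- **That the trial has no valid between-group test.** It has one in the interaction.

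**Conclusion.** The point holds as a recommended change of method; it does not show that the analysis is invalid. Treating a pre-randomisation measurement as an outcome level makes the group main effect estimate one-half to two-thirds of the week-8 effect. That result depends only on the assumed time course, not on the correlations. The main effect's power, about 18-25% or 29-40%, also depends on the assumed 0.8 SD and correlations.

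Adjusting for the pre-test narrows the CI relative to the change score in the cells examined. The power comparison with the interaction depends on the unknown time course, and the 9-point loss is the largest in these cells, not a bound.

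**What to change.** 1. Report as the main between-group result the EMS-minus-CON difference at week 8, adjusted for the pre-test value, with its 95% CI. Use ANCOVA or a model with baseline, arm, visit and arm-by-visit.
2. State that the group main effect of the mixed ANOVA is not read as the EMS effect.
3. Label one-way, within-arm results as descriptive, and say at which visits and over how many comparisons Bonferroni is applied.

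**Cost.** One covariate and a re-run on data already collected. If the effect was full by week 4, some power may be lost against the interaction. Because the SAP is written in the past tense, any choice of main test made now, including simply naming the interaction, should be labelled as a dated post hoc re-analysis and shown beside the original.

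**What it leaves open.** The Protocol lists 11 tests and names none as primary. Four of the 31 randomised participants (15 + 16) are missing from the 27 analysed (12 + 15). The change addresses neither.

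### The SAP applies Bonferroni to differences between two groups, which is a single pair, and does not say which family is corrected or which contrast of the arms follows the mixed ANOVA

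*SAP*

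**What the plan says.** The Protocol (Study Design) describes a trial "designed as a 2-arm parallel-group randomized controlled trial", with EMS and CON as the only groups. Testing took place "In the pre-, mid (week 4), and post (week 8) test periods", so each outcome has three visits. The first of these precedes allocation: "After completion of the pre-tests, participants were randomized into one of two exercise groups". Allocation was 15 to EMS and 16 to CON, and "the study was completed with 12 participants for the EMS group and 15 participants for the CON group".

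The SAP (Statistical Analysis) names the models: "One-way analysis of variance in repeated measures and Mixed Design Analysis of Variance in Repeated Measures were applied to the data". It then gives the sphericity rules and a single sentence on follow-up: "Bonferroni test was used to determine the intergroup differences". The significance level is 0.05. The section mentions no change score, no pre-test covariate, no group-by-time contrast and no family for the correction.

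**The concern.** That sentence is the only multiplicity correction in the section and the only follow-up that speaks of groups. Taken literally, it corrects over a factor with one pair, which does nothing. A reader who sees Bonferroni named may still assume that the arm comparisons are protected.

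The sentence also leaves open what is compared. Four readings fit the text:

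- **A.** Arm means averaged over the three visits.
- **B1.** Arms compared at week 4 and week 8, whatever the ANOVA shows.
- **B2.** The same tests, run only after a significant group-by-time result.
- **C.** *Intergroup* is loose wording for differences between visits.

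These have different error rates and different power, and the text does not allow a reader to choose among them. At stake is whether a statement that EMS differs from CON at a given visit rests on a comparison with known error that uses the pre-test properly.

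**Working it through.** **Inputs from the documents.** Two arms, three visits, alpha 0.05 (SAP). Allocation: "divided into EMS (n=15) and Control (CON) (n=16) groups". Completers: 12 EMS and 15 CON. The plan gives no figure of its own on this point to reproduce.

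**Assumptions, not in the documents.** Normal scores with SD 1, compound symmetry with within-person correlation r = 0.5, 0.7 or 0.8, two-sided tests, one outcome at a time. Where an effect is assumed, EMS gains an extra 0.4 SD by week 4 and 0.8 SD by week 8.

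**Step 1: what Bonferroni does in each family.**
- Arms: 2×1/2 = 1 pair; 0.05/1 = 0.05, no change.
- Arms at one visit: again 1 pair, no change unless the correction runs over visits.
- Visits: 3×2/2 = 3 pairs; 0.05/3 = 0.0167.

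**Step 2: reading A.** The extra gain averaged over visits is (0 + 0.4 + 0.8)/3 = 0.4 SD, because a third of the average is pre-randomisation data. The variance of a person's mean is (1 + 2r)/3, and 1/12 + 1/15 = 0.15. The noncentrality is 0.4/√[0.15(1 + 2r)/3] = 1.26, 1.15 and 1.11 for the three values of r. With 25 degrees of freedom, power is 23%, 20% and 19%. With no effect, the test rejects in 5%.

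**Step 3: group-by-time in the mixed ANOVA.** Centred over visits, the extra gain is −0.4, 0, 0.4. The noncentrality is (12×15/27) × (0.16 + 0 + 0.16)/(1 − r) = 4.27, 7.11 and 10.67. With F(2, 50), power is 42%, 63% and 82%.

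**Step 4: readings B1 and B2.** For two independent tests the null error would be 1 − 0.95² = 9.75%; correlation between visits brings it somewhat lower. Simulation (60,000 trials per setting) gives the figures in the table. For one level comparison at week 8, the noncentrality is 0.8/√0.15 = 2.07 and power is 51% at every r.

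**Step 5: the replacement.** ANCOVA on the pre-test at week 4 and week 8, each at 0.05/2 = 0.025, by the same simulation.

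| Follow-up | Null error, r = 0.5 / 0.7 / 0.8 | Power, 0.8 SD extra gain |
|---|---|---|
| A: arms averaged over visits | 5 / 5 / 5% | 23 / 20 / 19% |
| B1: level tests at week 4 or 8, no gate | 9.2 / 8.5 / 7.8% | 51% (week 8 alone) |
| B2: the same, after significant group-by-time | 1.5 / 1.0 / 0.8% | 30 / 39 / 45% |
| Replacement: ANCOVA at either visit, 0.025 each | about 5% | 53 / 70 / 84% |

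**Step 6: reading C.** The three visit pairs are properly corrected, but no follow-up compares the arms beyond group-by-time itself.

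**Step 7: a persistent arm difference.** Suppose the exclusions left a 0.5 SD difference present at all visits, with no EMS effect. Reading A then rejects in 27 to 33%, a week-8 level test in 24%, a single week-8 ANCOVA at 0.05 in 7 to 11%, and the week-8 difference in change in 5%.

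**The case against.** The strongest reply is that the mixed ANOVA already compares change between arms through group-by-time, so the trial has a valid test of effect and the sentence is only loosely worded. The first part stands in full: it would be wrong to say that the plan documents no comparison of arms. But with three visits, group-by-time is an omnibus test. It does not say at which visit the arms differ, or in which direction. That is the follow-up's job.

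A reader might infer three stronger things that the documents do not support.

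- *The follow-up compares levels, not change.* The SAP says neither. Under reading C it does not compare arms at all, and the one-way repeated-measures ANOVA over visits makes C plausible.
- *The plan inflates false positives.* Only B1 does. Reading A holds 5%, and a gate, which the SAP neither states nor excludes, takes the level tests well below 5%. It is true that a chance pre-test gap above 0.5 SD arises in about 20% of trials, half in each direction, and that when EMS is ahead reading A falsely favours EMS in 21 to 24%. But that rate applies only to those trials and is already counted within the overall 5%.
- *Level tests are always weaker.* At r = 0.5 the ungated week-8 level test has 51% power, against 42% for group-by-time.

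It can also be said that naming group-by-time and the correction family would be enough, and that ANCOVA is a preference. That is the minimum repair. It would still leave the visit-specific comparison of arms undefined.

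**Conclusion.** The point holds as a defect in the follow-up, not in the model. Without any assumption: Bonferroni over two groups corrects one pair and changes nothing, and the SAP states neither the family, nor the effect term, nor a contrast of arms on change or adjusted for the pre-test.

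The consequence varies by reading: low power (A), modest error inflation (B1), a conservative and underpowered test (B2), or no visit-specific comparison of arms (C). The percentages rest on the assumed correlations, effect size and linear shape, since the documents give no SDs or correlations; they show orders of magnitude only. This should be fixed, but it does not invalidate the group-by-time test.

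The unequal exclusions (12 of 15 against 15 of 16 retained) and multiplicity over the 11 tests on the three practice cards (4 + 4 + 3) are separate issues that this sentence neither causes nor cures.

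**What to change.** Name group-by-time in the mixed ANOVA as the omnibus test of effect, and replace the Bonferroni sentence with:

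> For each outcome with a numeric score, EMS and CON are compared at week 4 and week 8 by the EMS-minus-CON difference adjusted for the pre-test (ANCOVA), with p-values and confidence intervals Bonferroni-adjusted over these two visits. The difference in change from the pre-test is reported as a sensitivity analysis. Comparisons between visits within an arm are Bonferroni-adjusted over three pairs and are descriptive.

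If differences between visits were meant, correct the word *intergroup* as well. The Protocol describes no numeric score for the deep squat, so that test needs its own method.

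**Cost.** No new data are needed: two ANCOVAs per outcome on scores already collected. The change must be disclosed as made after the study was completed. Power at the adjusted level is 53 to 84% for a 0.8 SD extra gain, so a non-significant result is not evidence of no effect. ANCOVA is not immune to a persistent arm difference left by the exclusions (7 to 11% rejection at week 8 in the scenario above, against 5% for difference in change), which is why both are reported.
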